#### 12. Questions

Any questions related to the future biomedical research should be emailed directly to [contact].

## **10.7** Appendix 7: Country-specific Requirements

Not Applicable

## **10.8 Appendix 8: Blood Volume Table**

All Participants	Screening/ Baseline	Intervention	Poststudy	Total Collections	mL Per Collection	Total mL/ Test
Laboratory Safety Tests	2	4	1	7	6	42
HIV/Hepatitis Screen (at the discretion of the investigator)	1			1	5	5
Blood for Genetic Analysis		1		1	8.5	8.5
Blood for Exploratory Plasma Biomarkers for AD Diagnosis		1		1	18	18
Blood for MK-8189 and/or Metabolites Assay		10		10	4	40
Blood for Plasma Donepezil Assay		5		5	3	15
Blood for Plasma Memantine Assay		5		5	3	15
Total Blood Volume per Participant a						
a If additional pharmacokinetic/pharmacodynamic and/or safety analysis is necessary, additional blood (up to 50 mL)						

may be obtained.

#### 10.9 Appendix 9: Algorithm for Assessing Out of Range Laboratory Values

For all laboratory values obtained at prestudy (screening) visit and/or predose evaluation:

- A. If all protocol-specified laboratory values are normal, the participant may enter the study.
- B. If a protocol specified laboratory value is outside of the parameter(s) outlined in the inclusion/exclusion criteria (including a repeat if performed), the participant will be excluded from the study.
- C. If  $\geq 1$  protocol-specified laboratory value not specified in the inclusion/exclusion criteria is outside the normal range, the following choices are available:
  - a. The participant may be excluded from the study;
  - b. The participant may be included in the study if the abnormal value(s) is NCS (the investigator must annotate the laboratory value "NCS" on the laboratory safety test source document).
  - c. The participant may be included in the study if the abnormality is consistent with a pre-existing medical condition which is not excluded per protocol (eg, elevated eosinophil count in a participant with asthma or seasonal allergies), the medical condition should be annotated on the laboratory report.

OR

- d. The abnormal test may be repeated (refer items a. and b. below for continuation of algorithm for repeated values).
  - a. If the repeat test value is within the normal range, the participant may enter the study.
  - b. If the repeat test value is still abnormal, the study investigator will evaluate the potential participant with a complete history and physical examination, looking especially for diseases that could result in the abnormal laboratory value in question. If such diseases can be ruled out, and if the abnormal laboratory value is not clinically relevant, then the participant may enter the study.
- D. If there is any clinical uncertainty regarding the significance of an abnormal value, the participant will be excluded from the study.

#### 10.10 Appendix 10: General (Full) and Targeted Neurological Exam

The General (Full) and Targeted Neurological Examination will be performed at the time points specified in the Schedule of Activities (Section 1.3).

Note to the investigator: If at any time abnormalities are observed in the General or Targeted Neurological Exams, the Investigator should do additional examinations as needed based on his or her medical judgment.

#### The General (Full) Neurological Examination

The General (Full) Neurological Examination includes all of the modules listed below and is intended to be a general screening examination.

## **MODULE 1 – MENTAL STATUS EXAMINATION**

- A. General Level of Arousal: Generally assess general level of alertness, attentiveness, and concentration throughout the interview. Regarding attentiveness, note evidence of impaired attention or concentration. For example, difficulty remembering or following instructions or distractibility may be signs of inattention.
- B. Thought Processes and Language: Generally assess logic, relevance, organization and coherence of volunteer's use of language throughout the interview.
- C. Orientation (time, place, person)
- D. Attention/Concentration

Ask the subject to count backwards from 100 by 7's ("Serial 7's") or ask to recite months backwards or spell a 5 unique letter word (e.g. "WORLD") backwards.

Note: to avoid learning effects, switch between tests throughout the study

E. Memory: Test registration of 3 objects; then test immediate recall 5 minutes later.

# Grade: NORMAL or IMPAIRED and describe abnormality (for each, A to E, above). Normal performance on Serial 7's is getting to 65 with no more than one error.

## **MODULE 2 – CRANIAL NERVE ASSESSMENT**

- A.  $\underline{II}$  Visual Fields and acuity
- B. II, III Pupil Size and Reactivity
- C. III, IV, VI Extraocular Movements (range of motion, smooth pursuit, saccades, nystagmus)

- 1. Observe for nystagmus during eye movements, increased nystagmus at the end of gaze or other oculomotor changes (mild nystagmus at extremes of gaze is normal). Note direction of nystagmus
- D.  $\underline{V}$  Facial Sensation, Jaw Strength
- E. VII Muscles of Facial Expression (wrinkle brow, squeeze eyes shut, smile)
- F. VIII Auditory Acuity (assessed using a bed-side screening test e.g. by rubbing fingers on each side of subject's head or by whispering numbers)
- G.  $\underline{IX}$  Gag reflex
- H.  $\underline{X}$  Swallow
- I.  $\underline{XI}$  Shoulder shrug
- J. Tongue Protrusion (midline)

Score: left and right (except for G, H, J)

#### **Grade:** NORMAL or IMPAIRED and describe abnormality

#### **MODULE 3 - MOTOR SYSTEM**

#### A. Muscle Tone

- 1. Ask the volunteer to relax.
- 2. Flex and extend the volunteer's elbows and at the knees (bilaterally).
- 3. There is a small, continuous resistance to passive movement.
- 4. Observe for involuntary movements (e.g., tremor, tics, fasciculations). Observe for resistance to passive movement; observe for decreased (flaccid) or increased (rigid/spastic) tone.

Score: left and right

## **Grade:** NORMAL, INCREASED or DECREASED

- B. Muscle Strength
  - 1. Ask the subject to stand up from sitting without using hands

## **Grade:** NORMAL, IMPAIRED and describe abnormality

2. Test proximal limb strength by having the volunteer flex and extend the knees and elbows against your resistance.

Test bilaterally, and compare one side to the other.

Score: left and right

Grade: 5/5: normal;

4/5: movement against resistance impaired;

3/5: movement against gravity but not against resistance;

2/5: visible movement but not against gravity;

1/5: visible contraction;

0/5: no visible activity

3. Test distal limb strength by having the volunteer conduct dorsiflexion and plantar flexion of the volunteer's feet; finger abduction and handgrip strength against your resistance.

Test bilaterally, and compare one side to the other.

Score: left and right

Grade: 5/5: normal;

4/5: movement against resistance impaired;

3/5: movement against gravity but not against resistance;

2/5: visible movement but not against gravity;

1/5: visible contraction;

0/5: no visible activity

- C. Pronator Drift
  - 1. Ask the volunteer to hold both arms straight forward with, palms up and eyes closed for  $\sim$ 10-15 seconds as tolerated; watch for how well the arm position is maintained.
  - 2. Instruct the volunteer to keep both arms still while you tap them briskly downward. The volunteer should normally be able to maintain extension and supination. Inability to maintain extension and supination (and drift into pronation) indicates an upper motor neuron deficit.

Score: left and right

## **Grade**: NORMAL or IMPAIRED and describe abnormality

#### **MODULE 4 - REFLEXES**

- A. Biceps
- B. Knee

*Note:* Other deep tendon reflexes may be tested at Investigator's discretion (e.g. elbow, wrist or Achilles tendon)

Score: left and right

#### Grade: NORMAL, INCREASED, DECREASED or ABSENT

C. Babinski

Score: left and right

**Grade:** NORMAL or ABNORMAL

## **MODULE 5 - COORDINATION AND GAIT**

#### A. Rapid, Rhythmic Alternating Movements

1. Testing each hand separately, ask the volunteer to tap the distal thumb with the tip of each finger, in sequence, as fast as possible.

Score: left and right

## **Grade:** NORMAL or IMPAIRED

Reminder: If the rapid alternate movements are disturbed, the subject will be asked to strike his hand on the thigh, raise the hand, turn it over and then strike the back of the hand down on the same place. (This test is impaired in cerebellar disease, extra pyramidal disease and upper MN weakness.)

- B. Point-to-Point Movements
  - 1. Ask the volunteer to touch your index finger and their nose alternately several times. Move your finger about as the volunteer performs this task.

Score: left and right

#### **Grade:** NORMAL or IMPAIRED

Reminder: If the point-to-point testing is disturbed, the subject will be asked to place one heel on the opposite knee and then run it down the shin to the big toe. Repeat this for both sides. (Impaired tests indicate cerebellar disease.)

#### C. Romberg

- 1. Ask the volunteer to stand with both feet together and eyes closed for 20 to 30 seconds without support.
- 2. Be prepared to catch the volunteer if they are unstable.

#### **Grade:** NORMAL or IMPAIRED

- D. Gait
  - 1. Ask the volunteer to walk across the room, turn and come back (assess posture, balance, swinging of arms and movement of the legs).

#### **Grade:** NORMAL or IMPAIRED and describe abnormality

2. Ask the volunteer to walk heel-to-toe in a straight line (tandem gait).

## **Grade**: NORMAL or IMPAIRED and describe abnormality

#### **MODULE 6 - SENSORY**

- A. Light touch sense: cotton wisp on skin of forearms and legs, bilaterally.
- B. Pin prick: safety pin touched lightly to skin of forearms and legs, bilaterally.
- C. Temperature: warm or cool object touched to skin of forearms and legs, bilaterally.
- D. Vibration: tuning fork vibration detection in hands, feet bilaterally.
- E. Position sense: perception of thumb and toe movement, bilaterally.
- F. Stereognosis: (identify common objects placed in hand, e.g., coin, key).

#### Score: left and right

#### **Grade:** NORMAL OR IMPAIRED and describe abnormality (for each A to F)

#### **Targeted Neurological Exam**

The **Targeted Neurological Examination**, which is intended to focus on tests where drug effects can be seen, includes the following tests only:

#### **MODULE 1 – MENTAL STATUS EXAMINATION**

A. General Level of Arousal: Generally assess general level of alertness, attentiveness, and concentration throughout the interview. Regarding attentiveness, note evidence of impaired attention or concentration. For example difficulty remembering or following instructions or distractibility may be signs of inattention)

#### MODULE 2 – CRANIAL NERVE ASSESSMENT

- B. II, III Pupil Size and Reactivity
- C. III, IV, VI Extraocular Movements (range of motion, smooth pursuit, saccades, nystagmus)
  - 1. Observe for nystagmus during eye movements, increased nystagmus at the end of gaze or other oculomotor changes (mild nystagmus at extremes of gaze is normal). Note direction of nystagmus

## **MODULE 3 - MOTOR SYSTEM**

- B. Muscle Tone
  - 1. Ask the volunteer to relax.
  - 2. Flex and extend the volunteer's elbows (may also move wrists simultaneously) and at the knees (bilaterally). When testing the upper limbs, do this again while the subject makes large repetitive movements with the opposite arm (e.g. patting the palm of the hand on the knee).
  - 3. There is a small, continuous resistance to passive movement.

Score: left and right

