## 8.3.12 Neurological Exam

The General (Full) Neurological Exam will be performed at the Screening and Baseline visits. The Targeted Neurological Exam will be administered at times specified in the SoA.

The General and Targeted Neurological Exams are contained in Appendix 10.

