#### Events meeting the AE definition

- Any abnormal laboratory test results (hematology, clinical chemistry, or urinalysis) or other safety assessments (eg, ECG, radiological scans, vital signs measurements), including those that worsen from baseline, considered clinically significant in the medical and scientific judgment of the investigator.
- Exacerbation of a chronic or intermittent preexisting condition including either an increase in frequency and/or intensity of the condition.
- New conditions detected or diagnosed after study intervention administration even though it may have been present before the start of the study.
- Signs, symptoms, or the clinical sequelae of a suspected drug-drug interaction.
- Signs, symptoms, or the clinical sequelae of a suspected overdose of either study intervention or a concomitant medication.
- For all reports of overdose (whether accidental or intentional) with an associated AE, the AE term should reflect the clinical symptoms or abnormal test result. An overdose without any associated clinical symptoms or abnormal laboratory results is reported using the terminology "accidental or intentional overdose without adverse effect."
- Any new cancer or progression of existing cancer.

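### Muscle tone is tested with an opposite-arm activation step at every neurological exam after dosing but at none before it, so a finding seen only on activation has no matched baseline

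*Combined protocol and SAP*

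**What the plan says.** Section 8.3.12 assigns the two exams to different parts of the study: "The General (Full) Neurological Exam will be performed at the Screening and Baseline visits", and "The Targeted Neurological Exam will be administered at times specified in the SoA". In the Schedule of Activities (Section 1.3) the targeted exam is marked at Visits 5, 7, 8, 9 and 10, which are Days 7, 14, 21, 28 and poststudy. It is blank at Screening and Baseline.

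Appendix 10 (Section 10.10) gives the content. The full exam "includes all of the modules listed below and is intended to be a general screening examination". Its Module 3 tone item asks the participant to relax and then instructs: "Flex and extend the volunteer's elbows and at the knees (bilaterally". It has no activation step. The targeted exam, "which is intended to focus on tests where drug effects can be seen, includes the following tests only", has the same relaxed passive test in its Module 3 and then adds: "When testing the upper limbs, do this again while the subject makes large repetitive movements with the opposite arm".

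Two entries in Section 10.3.1 bear on what happens to a finding. One counts as adverse events "New conditions detected or diagnosed after study intervention administration even though it may have been present before the start of the study". The other covers abnormal results on safety assessments, provided the investigator considers them clinically significant. Section 9.4 makes all adverse events the primary safety endpoint. Under Section 4.1, adverse event data from about 8 participants with about 3 weeks of dosing inform the choice of regimen for later participants.

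**The concern.** A targeted exam is normally a subset of the full one, so that every on-treatment item has a pre-dose counterpart. For muscle tone this fails: the shorter exam contains a manoeuvre that the longer one lacks, and the change of technique coincides with the start of treatment. If an investigator finds increased tone on activation at Day 7, the neurological exam record cannot show whether the same manoeuvre would have given the same result at Baseline.

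This matters because tone is relevant to the drug. Section 4.2.1.2 says that extrapyramidal symptoms have been observed in the MK-8189 program, and Section 8.4.7 makes severe extrapyramidal symptoms, or those leading to discontinuation, events of clinical interest. A pre-existing sign that is first elicited after dosing could enter the adverse event data that form the primary endpoint and feed the early regimen review.

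**Working it through.** No power, alpha or sample-size figure bears on this point (Section 9.9 gives no power calculation), so the check is a side-by-side reading and a count.

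**Step 1. The tone procedure in each exam (Appendix 10, Module 3).**

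| | Full exam | Targeted exam |
|---|---|---|
| Relaxed passive flexion and extension, elbows and knees | Yes | Yes |
| Upper limbs repeated with opposite-arm movement | No | Yes |

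**Step 2. When each exam is done (Section 8.3.12 and the Schedule of Activities).**

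| | Screening | Baseline | Day 7 | Day 14 | Day 21 | Day 28 | Poststudy |
|---|---|---|---|---|---|---|---|
| Exam | Full | Full | Targeted | Targeted | Targeted | Targeted | Targeted |
| Activated tone tested | No | No | Yes | Yes | Yes | Yes | Yes |

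Count: 0 of 2 before the first dose; 4 + 1 = 5 of 5 after it (four in the intervention period, one poststudy). No participant has a scheduled pre-dose reading of activated tone.

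**Step 3. The route to the primary endpoint.** A sign found only on activation is first detected after dosing. Section 10.3.1 does not excuse it because it may have existed earlier. As an abnormal safety assessment, however, it becomes an adverse event only if judged clinically significant. Recording is possible, not automatic, and the judgement has to be made without the matched pre-dose reading.

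**Step 4. The early review.** By about 3 weeks each participant has had up to 3 targeted exams (Days 7, 14 and 21), so about 8 participants contribute up to 8 × 3 = 24 exams with activation, against none before dosing. Section 4.2 plans 21 on MK-8189 and 7 on placebo. If that ratio held among the first 8, which the documents do not guarantee, about 8 × 7/28 = 2 would be on placebo, too few to show the background rate of such findings.

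**Step 5. Effect of the fix.** Adding the step to the full exam gives 2 matched pre-dose readings. Doing the targeted tone item at Visit 2 gives 1. Neither changes the sample size.

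**The case against.** The case on the other side is substantial, and most of it stands as a limit on the weight of the point.

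- **Clinical significance filter.** Mild tone change seen only on activation, without symptoms, is a weak candidate for an adverse event. Section 10.3.4 also asks for a diagnosis rather than separate signs where one can be made. This stands; the claim is only that such a finding can be recorded.
- **Same exams in both arms.** A reader might infer that the comparison with placebo is biased. The documents do not support that: the exams and schedule are identical in both arms, so the expected difference is unaffected. Only the absolute count is exposed.
- **Another baseline for rigidity exists.** The Simpson Angus Scale covers rigidity and is done at Baseline and on treatment. This is real mitigation but partial: its technique is left to the Manual of Assessments, and the protocol does not say that it uses an activation manoeuvre.
- **Eligibility.** Clinically relevant parkinsonism and previous severe extrapyramidal symptoms are excluded (Section 5.2, criteria 4 and 13). That lowers the chance of pre-existing rigidity. It does not remove it, since participants may enter after antipsychotic washout (Section 5.1, criterion 10) and the neurological exam at Screening omits the activation step.
- **Extra examinations.** Appendix 10 lets the investigator examine further, but that note is triggered by an abnormality already seen.

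A reader might also notice that the targeted tone item omits the full exam's instruction "Observe for involuntary movements (e.g., tremor, tics, fasciculations" and infer that drug-related movements would be missed. The documents do not support that as a material gap. The AIMS and the Simpson Angus Scale are scheduled at Baseline and on Days 7, 14, 21 and 28, and largely cover it. At poststudy they are required only after a clinically meaningful change on Day 28.

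**Conclusion.** The mismatch is confirmed by the text and is minor. Activated muscle tone is examined at 0 of 2 pre-dose and 5 of 5 post-dose exams, so a finding seen only on activation has no like-for-like baseline. The exposure is to the absolute count of extrapyramidal-type findings and, through the investigator's judgement, to the adverse event count in the final report and in the review after about 8 participants.

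The consequence rests on one assumption that the documents do not state: that activation can bring out tone changes which relaxed passive testing misses. Rigidity evident at rest would be found by the full exam and is not at issue. The number of participants affected cannot be derived, because the documents give no prevalence of increased tone on activation in this population. A reader might take the dystonia rate reported for the Phase 2 study P005 as a yardstick, but that is a rate of reported adverse events in another study, not of tone signs on examination, and Section 4.3 places P005 in schizophrenia. Sections 9.4 and 9.6 plan no change-from-baseline summary of the neurological exam, so the effect on the analysis runs only through recorded adverse events.

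**What to change.** In Appendix 10, make the tone procedure the same before and after dosing, by either route:

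- add the opposite-arm activation step to the Muscle Tone item of the full exam, so that it is done at Screening and Baseline; or
- perform the targeted exam's Module 3 tone item at Baseline (Visit 2) and mark it in the Schedule of Activities.

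Then state, in Section 8.3.12 or Appendix 10, that this pre-dose reading is the reference for on-treatment tone findings, including when the investigator decides whether a finding is new or worse. The first route is simpler, since it adds nothing to the schedule.

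The cost is a short wording change and, by estimate, about a minute at a visit where a neurological exam already takes place. No visit, sample-size or treatment change is needed. Participants already past Baseline when the change is made would still lack the matched reading.

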## **Grade:** NORMAL, IMPAIRED, or DECREASED and describe abnormality

## **MODULE 5 - COORDINATION AND GAIT**

- A. Rapid, Rhythmic Alternating Movements
  - 1. Testing each hand separately, ask the volunteer to tap the distal thumb with the tip of each finger, in sequence, as fast as possible.

Score: left and right

## **Grade:** NORMAL or IMPAIRED

Reminder: If the rapid alternate movements are disturbed, the subject will be asked to strike his hand on the thigh, raise the hand, turn it over and then strike the back of the hand down on the same place. (This test is impaired in cerebellar disease, extra pyramidal disease and upper MN weakness.)

D. Gait

2. Ask the volunteer to walk heel-to-toe in a straight line (tandem gait).

## *Grade*: NORMAL or IMPAIRED and describe abnormality

#### **MODULE 6 - SENSORY**

A. Light touch sense: cotton wisp on skin of forearms and legs, bilaterally.
Abbreviation	Expanded Term
ADME	absorption, distribution, metabolism, and excretion
AE	adverse event
AIMS	Abnormal Involuntary Movement Scale
ALP	alkaline phosphatase
ALT	alanine aminotransferase
AST	aspartate aminotransferase
AUC	area under the curve
BARS	Barnes Akathisia Rating Scale
BDS	blood drug screen
BID	twice daily
BMI	body mass index
BP	blood pressure
CCU	Cardiac care unit
CI	confidence interval
Cmax	maximum plasma concentration
CNS	central nervous system
CL	clearance
CrCl	creatinine clearance
CR	complete response
CRF	Case Report Form
CRU	clinical research unit
C-SSRS	Columbia-Suicide Severity Rating Scale
CSR	Clinical Study Report
CTFG	Clinical Trial Facilitation Group
СҮР	cytochrome P450
DDI	drug-drug interaction
DILI	drug-induced liver injury
DNA	deoxyribonucleic acid
ECG	electrocardiogram
ECI	event of clinical interest
eCRF	electronic Case Report Form
EDC	electronic data collection
eGFR	estimated glomerular filtration rate
EMA	European Medicines Agency
EPS	Extrapyramidal Symptoms
FDA	Food and Drug Administration
FDAAA	Food and Drug Administration Amendments Act
FSH	follicle-stimulating hormone
GCP	Good Clinical Practice
GI	gastrointestinal
HBsAg	hepatitis B surface antigen

